### **5.5 Clinical data collection**

Demographic and clinical data routinely recorded during the initial evaluation will be used, including age, sex, relevant clinical history, and cardiovascular history. These variables will be used both for sample characterization and as potential covariates in the analytical models.

### **5.6 Anthropometric assessment and calculation of derived indices**

Anthropometric measurements will include weight, height, and waist circumference, obtained according to a standardized protocol. Body mass index (BMI) will be calculated as weight (kg) divided by height squared (m^2).

Waist circumference will be used as a marker of central adiposity and will be measured at the midpoint between the last rib and the iliac crest. Additionally, the body roundness index (BRI) will be calculated as a derived marker of body adiposity and central fat distribution, using the following formula:  $BRI = 364.2 - 365.5 \times \sqrt{1 - ((WC / 2\pi)^2 / (0.5 \times height)^2)}$ , where WC represents waist circumference in meters and height in meters [14].

BRI will be included in the analyzes as a continuous variable and may also be categorized into quartiles for the evaluation of its association with arterial stiffness parameters and morning blood pressure variables.

### **5.7 Office blood pressure measurement**

Office blood pressure will be measured by a trained professional using a validated automatic device (Microlife BP3AC1-1PC, Shenzhen, China), in an appropriate environment and after a period of rest. Three consecutive measurements will be obtained, performed on the same arm and under standardized conditions, and the mean of these measurements will be used for baseline blood pressure description and for the initial clinical characterization of the participants, in accordance with international recommendations for blood pressure measurement in humans [24].

### **5.8 Ambulatory blood pressure monitoring**

All participants will undergo 24-hour ambulatory blood pressure monitoring (ABPM) using a validated device (Dyna-MAPA monitor, Cardios, São Paulo, Brazil), with an appropriately sized cuff and preferably on the non-dominant arm. The device will be programmed to perform measurements every 20 minutes during the daytime period and every 30 minutes during the nighttime period. Daytime and nighttime periods will be defined based on the schedules reported by the participants in a sleep and activity diary. Only recordings with adequate quality will be considered valid, according to accepted criteria in guidelines and position statements on ABPM [25,26].

Blood pressure classification by ABPM will be based on the 24-hour mean, with ambulatory hypertension defined as a mean 24-hour BP  $\geq 130/80$  mmHg. Based on this classification, participants will be stratified into normotensive and untreated hypertensive groups for comparative and interaction analyses.

### **5.9 Definition of morning blood pressure parameters**

Morning systolic blood pressure (mSBP) and morning diastolic blood pressure (mDBP) will be calculated as the mean of the measurements obtained during the first two hours after awakening. Only recordings with at least two hours of valid measurements after awakening will be considered eligible for the calculation of morning parameters.

Sleep-through morning blood pressure surge (ST-MBPS) will be defined as the difference between mSBP and the lowest systolic blood pressure during the sleep period, considering this value and its adjacent readings, according to standardized definitions in the literature [17–19].

The prewaking morning blood pressure surge (PW-MBPS) will be defined as the difference between mSBP and the mean systolic blood pressure during the two hours preceding awakening. These two indices will be analyzed as complementary measures of morning blood pressure behavior.

### **5.10 Arterial stiffness assessment**

AS will be assessed by carotid–femoral pulse wave velocity (cfPWV) using the Complior Analyze device (ALAM Medical, Paris, France), with the participant in the supine position after at least 10 minutes of rest. Measurements will be performed in accordance with current recommendations for arterial stiffness research and clinical practice [27].

At least three consecutive measurements will be obtained per participant. For analysis, the mean of the closest measurements will be used, provided that the difference between them is equal to or less than 0.5 m/s, ensuring greater reproducibility and quality control of the assessment.

### 5.11 Laboratory assessment and acquisition of biochemical data

All patients included in the study must present laboratory tests previously performed as part of the clinical evaluation requested by the attending physician responsible for referral for ABPM. Biochemical tests will be performed after a fasting period of at least 8 hours, according to routine clinical practice, and will mandatorily include measurements of fasting glucose and plasma triglycerides.

Laboratory results will be obtained through reports presented by the participants at the time of evaluation. There is no direct intervention by the researchers in the request, selection of the laboratory, or performance of the tests, characterizing these data as originating from routine clinical practice, which may include both previously collected data and prospectively obtained data. This aspect reinforces the observational nature of the study and brings the findings closer to real-world conditions. Laboratory tests will be performed in certified clinical laboratories, following standardized diagnostic methods.

Laboratory and anthropometric parameters will be used for the calculation of metabolic indices associated with insulin resistance and cardiometabolic risk. The triglyceride–glucose (TyG) index will be calculated according to the following formula:  $TyG = \ln [TG \text{ (mg/dL)} \times \text{fasting glucose (mg/dL)} / 2]$ . From TyG, the following indices will be derived:  $TyG\text{-WC} = TyG \times \text{waist circumference (cm)}$ ;  $TyG\text{-BMI} = TyG \times \text{body mass index (kg/m}^2\text{)}$ ;  $TyG\text{-WHtR} = TyG \times [\text{waist circumference (cm)} / \text{height (cm)}]$  [9–13].

Additionally, composite metabolic indices independent of TyG will be calculated: METS-IR (metabolic score for insulin resistance):  $METS\text{-IR} = \ln [(2 \times \text{fasting glucose (mg/dL)}) + TG \text{ (mg/dL)}] \times BMI \text{ (kg/m}^2\text{)} / \ln [HDL\text{-C (mg/dL)}]$  [15]; CMI (cardiometabolic index):  $CMI = [\text{waist circumference (cm)} / \text{height (cm)}] \times [TG \text{ (mmol/L)} / HDL\text{-C (mmol/L)}]$  [16].

All indices will be analyzed as continuous variables and will also be categorized into quartiles for the evaluation of their association with arterial stiffness parameters and morning blood pressure variables.

### 5.12 Study variables

The main exposure variable will be represented by the TyG index and its derived metrics. The main vascular variable will be cfPWV. Secondary hemodynamic outcomes will include mSBP, mDBP, ST-MBPS, and PW-MBPS. Potentially confounding clinical variables, such as age, sex, BMI, waist circumference, mean 24-hour BP, and hypertension status, will be considered in the analytical models according to their pathophysiological relevance.

### **5.13 Sample size calculation**

The sample size calculation based on the primary objective, referring to the association between carotid–femoral pulse wave velocity and the triglyceride–glucose index, indicates a minimum requirement lower than the final planned sample. However, considering the secondary objectives of the study, which include the evaluation of morning blood pressure and morning blood pressure surge across quartiles of metabolic indices, with additional stratification between normotensive and untreated hypertensive individuals, a more robust sample size was chosen.

### **5.14 Statistical analysis**

Continuous variables will be described as mean and standard deviation or median and interquartile range, according to data distribution, while categorical variables will be presented as absolute frequencies and proportions. Normality will be assessed using appropriate methods prior to the selection of comparative tests.

For the analysis of secondary objectives, participants will be distributed into TyG quartiles. Comparisons between quartiles will be performed using analysis of variance (ANOVA) or the corresponding test, with calculation of *p* for trend when appropriate. Analyses may be repeated after stratification by hypertension status, in order to evaluate differential behavior of morning parameters between normotensive and untreated hypertensive individuals.

The association between cfPWV and TyG, as well as between TyG and morning BP parameters, will be evaluated using univariable and multivariable linear regression models. Covariates will be selected a priori based on biological plausibility and prior evidence, including age, sex, BMI, mean 24-hour systolic and diastolic BP, hypertension status, and other clinically relevant variables. Interaction terms will also be explored, particularly between TyG metrics and hypertension status.

Considering the analytical tradition of the group in arterial stiffness studies, additional methods of agreement and bias assessment may be employed to explore relationships between continuous variables when appropriate, including Lin's concordance correlation coefficient and Bland–Altman analysis. The level of statistical significance will be set at 5% in two-tailed tests.

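### Section 5.14 ties the secondary objectives to a covariate-free quartile ANOVA and writes an age- and sex-adjusted model only for TyG, not for the derived and composite indices

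*Protocol*

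**What the plan says.** Section 2.2 makes TyG-WC, TyG-BMI, TyG-WHtR, METS-IR and CMI secondary exposures, for cfPWV and for morning blood pressure and its surge. Section 5.11 says of the indices: "All indices will be analyzed as continuous variables and will also be categorized into quartiles".

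Section 5.14 then turns to the secondary objectives: "For the analysis of secondary objectives, participants will be distributed into TyG quartiles". The test follows: "Comparisons between quartiles will be performed using analysis of variance (ANOVA) or the corresponding test", with a trend p where appropriate. The analyses may be repeated by hypertension status. No covariate is attached to any of these steps.

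The next paragraph of 5.14 plans regression: "The association between cfPWV and TyG, as well as between TyG and morning BP parameters, will be evaluated using univariable and multivariable linear regression models". Its covariates are chosen in advance, "including age, sex, BMI, mean 24-hour systolic and diastolic BP, hypertension status, and other clinically relevant variables". Interaction terms between TyG metrics and hypertension status are to be explored.

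Section 5.12 states that "Potentially confounding clinical variables, such as age, sex, BMI, waist circumference, mean 24-hour BP, and hypertension status, will be considered in the analytical models".

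**The concern.** One-way ANOVA and its rank counterpart compare crude groups. If the quartiles of an index differ in age or sex, and the outcome depends on age or sex, the groups will differ even when the index has no association of its own. The protocol recognises both variables as potential confounders, yet the only test it links by name to the secondary objectives cannot account for them.

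The quartile comparison is not a side table. Section 5.13 gives the comparison of morning parameters across quartiles of the metabolic indices, further split by hypertension status, as the reason for planning a larger sample than the primary objective needs. A crude quartile result could therefore be read as the answer to a secondary objective. Section 2.2 also plans to compare the indices with one another, and a crude comparison would favour whichever index tracks age and sex most closely.

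**Working it through.** **Which analyses have a stated adjustment**

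| Exposure | Quartile comparison | Adjusted model expressly stated |
|---|---|---|
| TyG | 5.14 | Yes: 5.14, for cfPWV and morning BP |
| TyG-WC, TyG-BMI, TyG-WHtR | 5.11 | No; implied at most by 5.12 and by the interaction sentence in 5.14 |
| METS-IR, CMI | 5.11 | No |
| Repeats within hypertension strata | 5.14, optional | No; interaction terms for TyG metrics come closest |

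**How far a crude quartile test can mislead**

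The protocol gives no figure to reproduce. Section 5.14 supplies the two-sided 5% level. The sample sizes and correlations below are assumptions.

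Standardise the variables and let the index have no association with the outcome except through age. The crude correlation is then

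ρ = corr(age, index) × corr(age, outcome).

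For a normal index, the quartile means are ±1.271 and ±0.325 SD, so the variance between quartiles is v = (1.271² + 0.325²)/2 = 0.861. It follows that

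- the spurious difference between top and bottom quartile is 2 × 1.271 × ρ = 2.54ρ outcome SDs, whatever the sample size;
- the four-group F test has approximate noncentrality λ = nρ²v/(1 − ρ²v), on 3 and n − 4 degrees of freedom.

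Example: correlations 0.3 and 0.5 give ρ = 0.15. With n = 400, λ = 400 × 0.0225 × 0.861/(1 − 0.0225 × 0.861) = 7.9, and the F test rejects in 64%.

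False-positive rate of the crude quartile ANOVA, by formula, with simulation (2,000 runs) in brackets:

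| Age–index / age–outcome | ρ | Top minus bottom quartile | n = 100 | n = 200 | n = 400 |
|---|---|---|---|---|---|
| 0.1 / 0.2 | 0.02 | 0.05 SD | 5% (5%) | 5% (4%) | 6% (6%) |
| 0.2 / 0.5 | 0.10 | 0.25 SD | 10% (10.5%) | 17% (16%) | 31% (29%) |
| 0.3 / 0.5 | 0.15 | 0.38 SD | 18% (18%) | 35% (35%) | 64% (64%) |

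In the same simulated data, linear regression adjusted for age rejected in 4.8% to 5.6%.

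**Age and sex together, for a waist-based index**

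Assume the index correlates 0.3 with age and 0.4 with sex.

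- cfPWV, assumed to correlate 0.5 with age and 0.1 with sex: ρ = 0.3 × 0.5 + 0.4 × 0.1 = 0.19. The crude test rejects in 54% at n = 200 and 86% at n = 400 by formula (simulation 53% and 86%).
- Morning systolic pressure, assumed to correlate 0.2 with each: ρ = 0.3 × 0.2 + 0.4 × 0.2 = 0.14. Simulation gives 31% and 57%.

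The quartile test adjusted for age and sex stayed between 4% and 5% in these four settings.

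**The case against.** The strongest reply is that adjustment is already planned. A reader might infer from the ANOVA sentence that age and sex differences will be reported as effects of TyG. The documents do not support that. The next paragraph of 5.14 gives TyG a multivariable model with age and sex, for both cfPWV and morning blood pressure. TyG with cfPWV is also the primary objective, not a secondary one. A crude comparison beside an adjusted model is ordinary reporting. This part of the reply stands.

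For the derived metrics the reply stands in part. Section 5.12 says "The main exposure variable will be represented by the TyG index and its derived metrics" and that confounders will be considered in the models, and the interaction sentence in 5.14 speaks of TyG metrics in the plural. Regression of the derived metrics is a fair inference, but no sentence states it. METS-IR and CMI fall outside that definition of the main exposure.

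It can also be said that the ANOVA sentence concerns TyG quartiles only, so applying it to the other indices is as much an extension as applying the regression to them would be. That is a fair warning against reading 5.14 too firmly. On either reading, however, no adjusted model is expressly stated for the five other indices, while 5.11 and 5.13 do plan quartile comparisons of the indices.

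Lastly, the statistical analysis plan is not shown and may list the models. That would fill a gap, but the protocol does more than leave one: it names a covariate-free test for the secondary objectives and words its adjusted model for TyG alone.

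**Conclusion.** The point holds in limited form. For TyG-WC, TyG-BMI, TyG-WHtR, METS-IR and CMI, and for the optional stratified repeats, the protocol expressly states no age- and sex-adjusted model, and its named test for the secondary objectives carries no covariates. For TyG the only remaining issue is which of two planned analyses carries the conclusion.

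The size is illustrative. It runs from no material inflation to well over half of null comparisons declared significant, and depends on correlations and a sample size that the protocol does not give. The calculation also assumes roughly normal, linear relations. It would be wrong to read these rates as estimates for this study, or to infer that crude quartile tests will usually be falsely significant. It would be equally wrong to assume that men fill the top quartiles of the waist-based indices; nothing in the documents says so.

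**What to change.** In 5.14:

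1. State that the multivariable linear model, with at least age and sex, applies to every index in 5.11 and to any repeat within hypertension strata. The other covariates listed need a decision per index, since BMI is itself a component of TyG-BMI and METS-IR.
2. Take adjusted quartile means with 95% confidence intervals, and the trend p, from that model.
3. Label the crude quartile ANOVA as descriptive, and say that for TyG the adjusted regression carries the conclusion.

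The cost is a few sentences and slightly more analysis. Age and sex are already collected under 5.5. Some p-values will become less favourable than the crude ones.

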## **2. OBJECTIVES**

### **2.1 Primary objective**

To evaluate the association between arterial stiffness measured by carotid–femoral pulse wave velocity (cfPWV) and the triglyceride–glucose index.

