From a hemodynamic perspective, arterial stiffness (AS) may amplify this morning BP increase, since less compliant arteries have a reduced capacity to buffer the pulse wave, resulting in greater transmission of pulsatile pressure to the peripheral and microvascular circulation. In addition, metabolic dysfunction may interfere with autonomic regulation and baroreflex sensitivity, contributing to alterations in the circadian control of BP [22–23].

Despite the biological plausibility and clinical relevance of these interactions, the integrated relationship between metabolic indices derived from insulin resistance, anthropometric markers of central adiposity, arterial stiffness, and morning BP parameters remains insufficiently explored. Understanding these mechanisms may provide new insights

into the pathophysiology of hypertension in its early stages and contribute to the identification of phenotypes at higher cardiovascular risk, even in apparently normotensive individuals.

Therefore, the present study aims to evaluate the association between arterial stiffness, measured by cfPWV, and metabolic and anthropometric indices, including TyG and its derived metrics, BRI, METS-IR, and CMI, as well as to investigate their relationship with morning BP and MBPS, integrating metabolic, structural, and functional dimensions of cardiovascular pathophysiology.

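### Adjusting cfPWV for 24-hour systolic and diastolic BP together also adjusts for pulse pressure, a likely consequence of stiffness; MAP should carry the main adjusted model

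*Protocol*

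**What the plan says.** The primary objective (Protocol section 2.1) is: "To evaluate the association between arterial stiffness measured by carotid–femoral pulse wave velocity (cfPWV) and the triglyceride–glucose index". Section 5.14 says that this association, and that of TyG with the morning BP parameters, "will be evaluated using univariable and multivariable linear regression models". One covariate list, to be fixed in advance from plausibility and earlier findings, serves both outcomes. Its members are given as "including age, sex, BMI, mean 24-hour systolic and diastolic BP, hypertension status, and other clinically relevant variables". Neither the univariable nor the multivariable model is named as primary.

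Three other places bear on the role of BP in the cfPWV model:

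- Section 5.12 classes 24-hour BP with the confounders: "Potentially confounding clinical variables, such as age, sex, BMI, waist circumference, mean 24-hour BP, and hypertension status".
- Section 3 gives the mechanism the other way round: "less compliant arteries have a reduced capacity to buffer the pulse wave, resulting in greater transmission of pulsatile pressure".
- Section 5.8 derives hypertension status from the same 24-hour readings, "with ambulatory hypertension defined as a mean 24-hour BP" of at least 130/80 mmHg.

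The protocol does not separate the steady component of pressure from the pulsatile one. It does not discuss BP as a possible consequence of stiffness when it chooses covariates.

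**The concern.** Two pressures entered together carry two pieces of information: the level of pressure and the gap between systolic and diastolic. The level (MAP) distends the artery and affects measured cfPWV, so there is a good reason to hold it fixed. The gap (pulse pressure) is, on the protocol's own account of stiff arteries, something that stiffness produces. Holding a consequence of the outcome fixed is not confounder control: it removes part of the variation in cfPWV that the model is meant to explain, including part of what TyG explains.

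At stake is how the adjusted TyG slope for the primary objective is read. It would be reported as adjusted for confounders, although one component of the adjustment may lie downstream of cfPWV, and nothing in the stated list would show the reader how much that component matters.

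**Working it through.** The protocol states no sample size, slope, power or correlation, so there is no figure of its own to reproduce. The model structure comes from section 5.14 and the direction from stiffness to pulsatile pressure from section 3. Every numerical value below is an assumption.

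**Step 1: what the two pressures span.** With PP = SBP − DBP and MAP = DBP + PP/3, it follows that SBP = MAP + (2/3)PP and DBP = MAP − (1/3)PP. The pairs {SBP, DBP} and {MAP, PP} are invertible linear transforms of each other, so the TyG coefficient is identical under either. A simulated regression confirmed this: 0.1829 with SBP + DBP and 0.1829 with MAP + PP.

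**Step 2: PP purely downstream of cfPWV.** Let cfPWV = b·TyG + (age, MAP) + e and PP = c·cfPWV + (age, MAP) + v. Given the other covariates, the coefficient of PP is k = c·var(e) / [c²·var(e) + var(v)], and k·c = r², the squared partial correlation of PP with cfPWV. The TyG coefficient becomes b(1 − k·c) = b(1 − r²).

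The simulation used 400,000 records, standardised effects and a true slope of 0.20:

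| Assumed r | 1 − r² | Slope with MAP | Slope with SBP + DBP | Ratio | Loss by formula |
|---|---|---|---|---|---|
| 0.2 | 0.96 | 0.200 | 0.192 | 0.961 | 4% |
| 0.3 | 0.91 | 0.201 | 0.183 | 0.911 | 9% |
| 0.4 | 0.84 | 0.200 | 0.168 | 0.838 | 16% |
| 0.5 | 0.75 | 0.199 | 0.149 | 0.749 | 25% |

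Adding hypertension status to SBP + DBP left the slope unchanged to three decimals in every row.

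**Step 3: TyG also acts directly on PP.** Add d·TyG to the PP equation. The TyG coefficient is then b(1 − r²) − k·d. With b = 0.20, c = 0.3 and unit error variances, k = 0.3/1.09 = 0.275 and r² = 0.09/1.09 = 0.083, so the coefficient is 0.1835 − 0.275d.

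| d | Formula | Simulated |
|---|---|---|
| +0.1 | 0.156 | 0.156 |
| +0.3 | 0.101 | 0.101 |
| +0.8 | −0.037 | −0.037 |
| −0.1 | 0.211 | 0.210 |
| −0.3 | 0.266 | 0.267 |

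The slope is inflated when d is below −b·c, here −0.20 × 0.3 = −0.06. With a true null (b = 0), a purely downstream PP gives no bias, while d = +0.2 gives a spurious slope of about −0.05.

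**Step 4: PP as a marker of a shared cause.** When PP was not caused by cfPWV, but both shared a cause that also raised TyG, the slope moved from 0.311 with MAP to 0.297 with SBP + DBP, against a true 0.20. That fall removes some confounding and is not a bias.

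**The case against.** Four objections carry weight.

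- **The mechanism in section 3 is general.** The sentence concerns pulsatile pressure reaching the peripheral and microvascular circulation, and it explains why stiffness may amplify the morning rise. It does not name 24-hour brachial pulse pressure, and section 5.12 treats 24-hour BP as a potential confounder. This stands to the extent that pulse pressure can be called only a likely consequence of the outcome. It does not remove the tension between the two sections.
- **The objective is an association.** A TyG slope conditional on BP is a legitimate quantity. That is true, but the reader should then know that it is conditional on pulse pressure as well as on pressure level.
- **The list is open, and a statistical analysis plan may stage the models.** The absence of an intermediate model is therefore not counted as a defect. The point rests on what section 5.14 states, which is both pressures by name.
- **The size may be small.** At r of 0.3 or less the loss is under 10%.

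A reader might also infer several stronger claims that the documents do not support:

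- That SBP plus DBP amounts to adjusting for pulse pressure alone. It is MAP plus pulse pressure, and the MAP part is worth keeping.
- That the slope is always pulled toward zero. Steps 3 and 4 show otherwise.
- That power suffers materially. No sample size or effect is given. Residual variance shrinks too, so in step 2 the t ratio falls only by about √(1 − r²), to √0.96 = 0.98 at r = 0.2 and √0.91 = 0.95 at r = 0.3.
- That a null adjusted result could not be told from over-adjustment. Losses of 4% to 25% do not turn a real slope into zero, and the univariable slope is planned as well.
- That any part of the TyG association carried through BP counts against SBP plus DBP. A MAP-adjusted model would also remove a part carried through pressure level.

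**Conclusion.** The point holds in conditional form. The stated covariate list conditions the cfPWV model on pulse pressure; that follows exactly from the algebra. On the causal direction given in section 3, this is conditioning on a likely consequence of the outcome, at odds with the confounder label in section 5.12.

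If pulse pressure is purely downstream of cfPWV, the TyG slope loses 4% to 25% for assumed r between 0.2 and 0.5. With a direct effect of TyG on pulse pressure the bias can be larger or go the other way. If pulse pressure marks a shared cause, part of the change is legitimate. The protocol gives no r and does not settle which structure applies, so neither size nor direction can be stated as fact. The specification should nevertheless be changed, because a better one keeps control of distending pressure at almost no cost. Hypertension status, a threshold on the same readings, is at worst redundant as a covariate in the main model.

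**What to change.** In section 5.14, give the cfPWV outcome its own covariate statement, fixed before any slopes are seen:

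- **Main adjusted model:** age, sex, BMI and 24-hour MAP, computed from the 24-hour systolic and diastolic means already recorded.
- **Reported beside it:** the same model with no BP term, so that the pressure-related share of the TyG association is visible.
- **Sensitivity analysis:** 24-hour SBP and DBP together, with a sentence saying that this also conditions on pulse pressure.
- **Hypertension status:** only in the effect-modification model, as a main effect together with its interaction with TyG.

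The cost is a short change to section 5.14 and one or two extra regressions on data already collected. The downside is a slightly less flexible BP adjustment in the main model, which the sensitivity analysis covers. The covariates for the morning BP outcomes are a separate matter and are not touched by this change.

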### **3. THEORETICAL BACKGROUND**

Systemic arterial hypertension remains one of the main determinants of cardiovascular morbidity and mortality at a global level, showing a continuous and progressive relationship with adverse events, including myocardial infarction, stroke, and heart failure [1]. Evidence from large population-based studies demonstrates that even modest increases in blood pressure (BP) are associated with a significant increase in cardiovascular risk, reinforcing the need for more comprehensive risk stratification strategies beyond conventional office BP measurements [2–3].

In this context, the incorporation of vascular markers has enabled a better understanding of cardiovascular pathophysiology. Arterial stiffness (AS), particularly assessed by carotid–femoral pulse wave velocity (cfPWV), is considered the gold standard for the non-invasive evaluation of aortic stiffness and shows a strong independent association with cardiovascular events and mortality [4]. Increased cfPWV reflects structural and functional alterations of the arterial wall, including elastin fragmentation, increased collagen content, vascular calcification, and endothelial dysfunction, representing an integrated marker of cumulative vascular damage [5–6].

In parallel, insulin resistance plays a central role in the pathophysiology of cardiometabolic diseases. This metabolic state is associated with reduced nitric oxide bioavailability, increased sympathetic nervous system activity, chronic low-grade inflammation, and vascular remodeling, mechanisms directly involved in the development of arterial stiffness [7–8]. The triglyceride–glucose (TyG) index, derived from widely available laboratory parameters, has been validated as a reliable surrogate marker of insulin resistance, showing consistent associations with type 2 diabetes mellitus, subclinical atherosclerosis, and cardiovascular events [9–10].

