## **5.4 Inclusion and exclusion criteria**

Individuals who meet all of the following criteria will be included in the study:

- Age between 18 and 65 years;
- Both sexes;
- Referral for ambulatory blood pressure monitoring (ABPM) as part of clinical evaluation;
- Not using antihypertensive medication at the time of inclusion;
- Availability of complete office blood pressure data and valid ABPM recordings;
- Undergoing arterial stiffness assessment by carotid–femoral pulse wave velocity (cfPWV);
- Availability of laboratory tests including fasting glucose and triglycerides for calculation of the triglyceride–glucose (TyG) index;
- Agreement to participate in the study by signing the informed consent form (for prospective participants).

Individuals presenting any of the following conditions will be excluded from the study:  
Current use of antihypertensive medication;

- Cardiac arrhythmias that compromise the accuracy of blood pressure measurements or cfPWV;
  - ABPM recordings with inadequate quality or an insufficient number of valid measurements;
  - Clinical conditions that prevent or compromise adequate cfPWV measurement;
  - Severe vascular diseases or anatomical alterations that preclude pulse wave analysis;
  - Absence of essential data for calculation of metabolic indices or evaluation of the primary outcomes;
  - Refusal to participate in the study or absence of a signed informed consent form (for prospective data collection).

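### Section 5.14 names only TyG × hypertension as an interaction; without age × hypertension that exploratory test for cfPWV can pick up part of a difference in age slopes

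*Protocol*

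**What the plan says.** Protocol section 5.14 relates cfPWV to TyG, and TyG to the morning blood pressure parameters, in models that "will be evaluated using univariable and multivariable linear regression models". On adjustment it says "Covariates will be selected a priori based on biological plausibility and prior evidence, including age, sex, BMI, mean 24-hour systolic and diastolic BP, hypertension status". It adds that other clinically relevant variables may enter. The next sentence is "Interaction terms will also be explored, particularly between TyG metrics and hypertension status". Age × hypertension is neither named nor ruled out.

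Section 5.8 defines hypertension status from the 24-hour mean pressure and says "participants will be stratified into normotensive and untreated hypertensive groups for comparative and interaction analyses", without naming the outcome of those analyses. Section 5.14 also allows a stratified analysis, but as an option and for another outcome: "Analyses may be repeated after stratification by hypertension status, in order to evaluate differential behavior of morning parameters between normotensive and untreated hypertensive individuals". The test level is fixed by "The level of statistical significance will be set at 5% in two-tailed tests".

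**The concern.** A covariate entered only as a main effect is held to one slope across both hypertension groups. This is enough to remove its confounding from a common TyG slope. It is not enough for a TyG × hypertension term. If the covariate's own slope differs by group and the covariate is correlated with TyG, the unmodelled difference shows up partly as a difference in TyG slopes.

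Age is the obvious candidate. Eligibility spans a wide range ("Age between 18 and 65 years"), and section 3 describes raised cfPWV as "representing an integrated marker of cumulative vascular damage". That description makes a steeper rise with age under higher pressure plausible, though it does not establish one.

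At stake is whether a statement that TyG relates differently to stiffness in untreated hypertensive people reflects TyG or ageing. The bias is a property of the model and does not shrink with sample size, so the false-positive rate rises as the study grows.

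**Working it through.** The protocol gives no figure to reproduce. Section 5.13 states no number of participants, and no correlation, slope or standard deviation appears anywhere.

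**Inputs from the protocol:** linear regression; two-sided 5% test; age as a covariate; TyG × hypertension as the named interaction.

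**Assumed inputs (none in the documents):**
- age SD 12 years and TyG SD 0.6
- residual SD of cfPWV σ = 1.2 m/s
- half of participants hypertensive
- age–TyG correlation ρ of 0.2 to 0.3, equal in both groups
- age slope steeper in hypertensives by d = 0.02 to 0.04 m/s per year
- true TyG × hypertension effect zero

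**Bias.** With age as a main effect only, the TyG × hypertension coefficient is shifted by

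bias = d × ρ × SD(age) / SD(TyG).

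- Low end: 0.02 × 0.2 × 12 / 0.6 = 0.08 m/s per TyG unit.
- High end: 0.04 × 0.3 × 12 / 0.6 = 0.24 m/s per TyG unit.
- If d = 0 or ρ = 0, the bias is zero.

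**Rejection rate.** With equal groups the standard error of the interaction is about 2σ / (√n × SD(TyG)). The expected z-value is therefore d × ρ × SD(age) × √n / (2σ), and the TyG SD cancels.

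- n=300, low end: 0.02 × 0.2 × 12 × 17.32 / 2.4 = 0.35, so the test rejects in about 6.4% of studies.
- n=300, high end: 0.04 × 0.3 × 12 × 17.32 / 2.4 = 1.04, about 18%.
- n=800, low end: 0.02 × 0.2 × 12 × 28.28 / 2.4 = 0.57, about 8.7%.
- n=800, high end: 0.04 × 0.3 × 12 × 28.28 / 2.4 = 1.70, about 39%.

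**Simulation** under the same assumptions (1,500 runs per setting, error about ±1.1 points near 5%):

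| ρ | d | Bias by formula | n=200 | n=400 | n=800 |
|---|---|---|---|---|---|
| 0.2 | 0.02 | 0.08 | 5.1% | 7.5% | 8.1% |
| 0.2 | 0.04 | 0.16 | 8.5% | 11.4% | 19.9% |
| 0.3 | 0.02 | 0.12 | 6.9% | 9.1% | 14.9% |
| 0.3 | 0.04 | 0.24 | 12.5% | 22.7% | 38.5% |

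The simulated mean coefficients agree with the formula. In every setting with ρ = 0 or d = 0, rejection was 4.3–6.2%. With age × hypertension added, rejection was 4.3–6.2% throughout and the mean coefficient stayed within 0.02 of zero.

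**Cost of the extra term.** Adding age × hypertension inflates the standard error by 1/√(1 − ρ²). Take n=400, a true interaction of 0.6 m/s per TyG unit and d = 0. The standard error is 2.4 / (20 × 0.6) = 0.20, so the expected z is 3.0 and power is about 85.1%. At ρ = 0.2 the z becomes 3.0 × √0.96 = 2.94, with power about 83.6%, a loss of 1.5 points. At ρ = 0.3 it becomes 3.0 × √0.91 = 2.86, with power about 81.6%, a loss of 3.5 points.

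**The case against.** The strongest reply is that the protocol fixes no wrong model. It speaks of interaction terms in the plural, its wording singles out one without excluding others, and exact product terms are often left to an analysis plan, which is not shown here. That stands in part: a reader might infer that the protocol rules out age × hypertension, and it does not. What remains is that 5.14 sets out the covariates and singles out one product. An analyst following it would ordinarily fit the model without the age product.

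Second, no objective in section 2 concerns effect modification by hypertension. Where the protocol ties the hypertension strata to an outcome (sections 5.13 and 5.14), that outcome is morning pressure or surge. This limits the importance. It does not remove the point, because the interaction sentence follows directly on models that include cfPWV, and 5.8 forms the groups with interaction analyses in view.

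Third, neither premise is in the documents. This stands. Section 3 speaks of accumulated arterial damage, not of age slopes by hypertension status, and nothing in the protocol says that TyG rises with age. A reader might take the section 3 wording as proof of a steeper age slope in hypertensives; it only makes one plausible.

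**Conclusion.** The point holds as a conditional one. Two things must both be true: age and TyG are correlated within hypertension groups, and the age slope of cfPWV differs between groups. Then a TyG × hypertension test with age only as a main effect is biased. Only the share of the slope difference set by the correlation passes over. Under the assumptions above the bias is 0.08–0.24 m/s per TyG unit, and the false-positive rate is about 6–18% at n=300 and 9–39% at n=800. At the mild end (ρ = 0.2, d = 0.02) the inflation is small.

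Two stronger readings should be resisted. One is that the study will report a false effect modification: the figures show a raised risk, and even at the high end with n=800 most studies would not reject. The other is that the main TyG–cfPWV result is compromised: the mechanism concerns the interaction term, and the primary association was not examined here. This is a cheap improvement to an exploratory analysis, not an error in the primary one.

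**What to change.** Add to section 5.14: any model that tests a TyG metric by hypertension status for cfPWV also contains age × hypertension status, and effect modification by hypertension is not claimed unless it persists in that model.

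Products of sex and BMI with hypertension status can be optional sensitivity terms. BMI × hypertension should not be added when the metric is TyG-BMI, because that index is itself TyG multiplied by BMI and the two products would be entangled.

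The cost is one sentence and no new data. When the age slopes do not in fact differ, the extra term loses roughly 1–4 points of power. Adding the sex and BMI products as well cost about 7 points in a simulation at n=400 with a true interaction of 0.6, which is why they are better kept optional.
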